6.6. Dose Modifications

Treatment with erdafitinib should be discontinued or modified based on erdafitinib-related toxicity as described in Table 3. For eye, skin/nail, dry mouth/mucositis, and phosphate toxicity, specific recommendations in the management guidelines are provided in Section 6.6.1.

Erdafitinib- related Toxicity Grade	Action	Dose modification after resolution of AE
1	None	Continue same dose.
2	None, or consider interruption if the toxicity is considered clinically significant	If interrupted, restart at same dose if toxicity is completely resolved to baseline or consider restarting at 1 dose lower ^a if not completely resolved to baseline (but resolved to Grade 1).
3	Interrupt drug	Restart at 1 dose lower ^a if recovered to baseline (to \leq Grade 1 or back to baseline for non-hematologic toxicity) within 28 days; restart at 2 doses lower ^a if not completely resolved to baseline (but resolved to Grade 1) within 28 days. Discontinue drug if unresolved for >28 days.
4	Interrupt drug	Discontinue.

 Table 3:
 Erdafitinib Dose Modification Rules Based on Erdafitinib-related Toxicity Severity

^a Please refer to Table 4.

- Subjects with any grade of toxicity (Grade 1 to 4) should be provided symptomatic treatment where applicable.
- If erdafitinib is interrupted consecutively for 1 week or longer due to drug-related toxicity, the study drug may be reintroduced at either the same dose level or the first reduced dose level following recovery from the toxicity (see dose reduction levels in Table 4, Table 5, and Table 6). A second dose reduction may be implemented following a second occurrence of drug-related toxicity.
- If erdafitinib must be withheld for more than 28 days for a drug-related adverse event that fails to resolve to acceptable level (eg, ≤Grade 1 non-hematologic toxicity or back to baseline), treatment with erdafitinib should be discontinued except when the subject has been deriving benefit from treatment, and the investigator can demonstrate that continued treatment with erdafitinib is in the best interest of the subject. Erdafitinib may be re-started at the same or a lower dose (Table 4, Table 5, and Table 6) if the sponsor's medical monitor concurs with the assessment.
- If erdafitinib was dose-reduced and the adverse event that was the reason for this dosereduction has completely resolved, the dose may be re-escalated to the next higher dose if the subject was deriving benefit from treatment, and the investigator can demonstrate that dose re-escalation of erdafitinib is in the best interest of the subject and the sponsor's medical monitor concurs with the assessment.
- In all cases of clinically significant impaired wound healing or imminent surgery or potential bleeding complications, it is recommended that dose administration be interrupted, appropriate clinical laboratory data (eg, coagulation parameters) be carefully monitored, and supportive therapy administered, where applicable. Dose administration may be restarted when it is considered safe and at an appropriate dose, according to the investigator's assessment.

Category	No up-titration at Cycle 1 Day 14	With up-titration at Cycle 1 Day 14
	Dose	Dose
Starting dose	8 mg	8 mg
Up-titration at Cycle 1 Day 14	None	9 mg
1st dose reduction	6 mg	8 mg
2nd dose reduction	5 mg	6 mg
3rd dose reduction	4 mg	5 mg
4th dose reduction	stop	4 mg
5th dose reduction		stop

Table 4: Erdafitinib Dose Reduction Levels: Adults and Adolescents Aged ≥15 to <18 Years

For Cycle 1 Day 14			
Category		No up-titration at Cycle 1 Day 14	With up-titration at Cycle 1 Day 14
Starting Dose on Cycle 1	Day 1	5 mg	5 mg
Up-titration at Cycle 1 Day	y 14	None	6 mg
1st dose reduction		4 mg	5 mg
2nd dose reduction		3 mg	4 mg
3rd dose reduction		stop	3 mg
4 th dose reduction			stop
For Cycle 2 Day 7	A		
Category	No up-titration at Cycle 1 Day 14 and Cycle 2 Day 7	No up-titration at Cycle 1 Day 14 but with up- titration at Cycle 2 Day 7	Up-titration at Cycle 1 Day 14 followed by up- titration at Cycle 2 Day 7
Dose on Cycle 2 Day 7	5 mg	5 mg	6 mg
Up-titration at Cycle 2 Day 7	None	6 mg	8 mg
1st dose reduction	4 mg	5 mg	6 mg
2nd dose reduction	3 mg	4 mg	5 mg
3rd dose reduction	stop	3 mg	4 mg
4th dose reduction	6	stop	3 mg
5th dose reduction		1	stop

Table 5: Erdafitinib Dose Reduction Levels: Adolescents Aged ≥12 to <15 Years

For Cycle 1 Day 14			A REAL PROPERTY AND A REAL PROPERTY AND A
Category		No up-titration at Cycle 1 Day 14	With up-titration at Cycle 1 Day 14
Starting Dose on Cycle 1	Day 1	3 mg	3 mg
Up-titration at Cycle 1 Day	14	None	4 mg
1st dose reduction		stop	3 mg
2nd dose reduction			stop
For Cycle 2 Day 7			
Category	No up-titration at Cycle 1 Day 14 and Cycle 2 Day 7	No up-titration at Cycle 1 Day 14 but with up- titration at Cycle 2 Day 7	Up-titration at Cycle 1 Day 14 followed by up-titration at Cycle 2 Day 7
Dose on Cycle 1 Day 14	3 mg	3 mg	4 mg
Up-titration at Cycle 2 Day 7	None	4 mg	5 mg
1st dose reduction	stop	3 mg	4 mg
2nd dose reduction		stop	3 mg
3rd dose reduction			stop

Table 6: Erdafitinib Dose Reduction Levels: Children Aged ≥6 to <12 Years

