6.6.1.2. Guidelines for the Management of Dry Mouth and Mucositis

Guidelines for the clinical management of dry mouth (xerostomia) and mucositis are provided in Table 9 and Table 10, respectively.

General prophylaxis for dry mouth and oral mucositis:

- Good oral hygiene
- Use a soft toothbrush
- Avoidance of spicy, acidic, hard, and hot food and beverages
- Use of mild-flavored toothpastes
- Use of salt and baking soda mouthwashes 3 or 4 times per day
- Water soluble lubrication agents like artificial saliva (for xerostomia or dry mouth)

Grade and Definition	Study Drug (Erdafitinib) Management	Symptom Management
Grade 1: symptomatic (eg, dry or thick saliva) without significant dietary alteration; unstimulated saliva flow >0.2 mL/min	Continue erdafitinib at current dose.	Sorbitol lozenges as needed
Grade 2: moderate symptoms; oral intake alterations (eg, copious water, other lubricants, diet limited to purees or soft, moist foods); unstimulated saliva 0.1 to 0.2 mL/min	Continue erdafitinib at current dose.	Sorbitol lozenges as needed and Cevimeline 30 mg TID or Pilocarpine 5 mg TID, orally
Grade 3: inability to adequately aliment orally; tube feeding or TPN indicated; unstimulated saliva less than 0.1 mL/min	Hold erdafitinib (for up to 28 days), with weekly reassessments of clinical condition. When resolved to \leq Grade 1 or baseline, restart at 1 dose level below in consultation with the medical monitor.	Sorbitol lozenges as needed and Cevimeline 30 mg TID or Pilocarpine 5 mg TID, orally
Grade 4: life-threatening consequences, urgent intervention indicated	Discontinue erdafitinib.	Evaluation and therapy as clinically indicated

 Table 9:
 Guidelines for Management of Dry Mouth (Xerostomia)

Table 10:	Guidelines for	r the Management	of Oral Mucositis
1 4010 101	Guidennes io	i the management	or or ar macositis

Grade	Study Drug (Erdafitinib) Management	Symptom Management
Grade 1	Continue erdafitinib at current dose.	 Continue general prophylaxis recommendations Dexamethasone solution (0.5 mg/5mL solution) swish and spit QID or similar solution that is available in your country/territory and lidocaine 2-5% jelly or solution. Consider clotrimazole/nystatin if subjects are at risk of developing oral candidiasis.

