6.6.1.6. Guidelines for the Management of Dry Eye

- General considerations: Avoid unnecessary exposure to sunlight and use sunglasses in bright light.
- **Prophylactic management:** Frequent use of artificial tear substitutes and ocular demulcents is strongly recommended, ie, every 2 hours during awake time.
- Reactive management:
 - Withhold erdafitinib for Grade 3 toxicity
 - Artificial tear substitutes if not started, every 2 hours during awake time
 - Ocular demulcents
 - Severe treatment-related dry eye should be evaluated by an ophthalmologist

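### For Grade 3 toxicities with no guideline of their own in Section 6.6.1, Protocol Table 3 requires a reduced restart dose, but the 1-week bullet in Section 6.6 permits the same dose.

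*Protocol*

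**What the plan says.** Protocol Section 6.6 opens with a general rule: "Treatment with erdafitinib should be discontinued or modified based on erdafitinib-related toxicity as described in Table 3". It then points to Section 6.6.1 for eye, skin and nail, mouth and phosphate toxicity.

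For Grade 3, Table 3 says to interrupt the drug. If the event recovers within 28 days the instruction is "Restart at 1 dose lower". If it has resolved only to Grade 1, the restart is two doses lower. The Grade 3 row has no same-dose option. The Grade 2 row does have one, for events that have fully resolved.

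One of the bullets under the table has its own trigger: "If erdafitinib is interrupted consecutively for 1 week or longer due to drug-related toxicity". After such a hold, "the study drug may be reintroduced at either the same dose level or the first reduced dose level following recovery from the toxicity". The bullet mentions no grade. Its next sentence ties a second reduction to a second occurrence of toxicity.

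Section 6.6.1 sets Grade 3 restart doses for the toxicities it covers. For dry mouth, for example, the subject should "restart at 1 dose level below in consultation with the medical monitor".

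**The concern.** A Grade 3 diarrhea or asthenia held for ten days and then recovered meets both rules. Table 3 requires a lower dose, and the bullet allows the dose at which the severe event occurred. Two sites could treat the same event differently and both claim to follow Section 6.6.

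The stake is subject safety and consistent dosing. It also touches deviation reporting: SAP Section 4.5 lists incorrect dosing as a category of major deviation, and the text does not settle whether a same-dose restart after a Grade 3 event belongs there.

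**Working it through.** No sample size, power or alpha figure is involved. The check compares the two rules and reads the dose levels from Tables 4 to 6.

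**Step 1: which events are in scope.** Seven tables in Section 6.6.1 give a Grade 3 restart dose: phosphate (Table 8), dry mouth (9), oral mucositis (10), dry skin (11), nail toxicity (13), paronychia (14) and eye toxicity (15). Those events have their own rule. Toxicities without a guideline there fall to Table 3 and the bullets. Section 2.2.1 shows that these are not rare kinds of event: diarrhea was reported in 51% of subjects in the Phase 2 urothelial study and asthenia in 45% in the Phase 1 study. Neither figure is split by grade.

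**Step 2: the two rules side by side, for a Grade 3 event held 1 week or longer and recovered within 28 days.**

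| | Table 3 | 1-week bullet |
|---|---|---|
| Recovered to baseline | 1 dose lower | Same dose or first reduced level |
| Resolved only to Grade 1 | 2 doses lower | Same dose or first reduced level |
| Second level of reduction | After one incompletely resolved event | After a second occurrence |
| Grade limit | Specific to Grade 3 | None |

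Table 3 itself blurs the line between one and two levels for non-hematologic events, because a parenthesis in its first clause counts recovery to Grade 1 or less as recovery. This does not affect the point: neither branch allows the same dose.

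**Step 3: what the difference is in milligrams.** The percentage is 1 − (lower dose ÷ current dose), for one level.

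| Age group (source) | Dose at event = bullet's same-dose option | Table 3, 1 lower | Reduction forgone | Table 3, 2 lower |
|---|---|---|---|---|
| Adults and ≥15 years (Table 4) | 9 mg | 8 mg | 1 − 8/9 = 11.1% | 6 mg |
| | 8 mg, not up-titrated | 6 mg | 1 − 6/8 = 25.0% | 5 mg |
| 12 to <15 years (Table 5) | 8 mg | 6 mg | 1 − 6/8 = 25.0% | 5 mg |
| | 6 mg | 5 mg | 1 − 5/6 = 16.7% | 4 mg |
| | 5 mg | 4 mg | 1 − 4/5 = 20.0% | 3 mg |
| 6 to <12 years (Table 6) | 5 mg | 4 mg | 1 − 4/5 = 20.0% | 3 mg |
| | 4 mg | 3 mg | 1 − 3/4 = 25.0% | stop |
| | 3 mg | stop | 100% | stop |

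The 3 mg row should be uncommon after Day 14. Section 4.3 predicts that about 96% of children in this age group are up-titrated then, which leaves 100% − 96% = about 4%. That prediction comes from a simulation that the protocol itself says to treat with caution. The row also covers children before the Day 14 decision and any child already reduced to 3 mg.

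**Step 4: which rule is likely intended.** Of the seven Section 6.6.1 tables with a Grade 3 restart dose, five restart one level lower (Tables 9, 10, 11, 13 and 14), one restarts two levels lower if appropriate (Table 15) and one restarts at the same dose (Table 8, phosphate). The pattern points to a reduction, with phosphate as the stated exception.

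**The case against.** The best defence is that this is loose drafting and not a contradiction. The lead-in names Table 3 as the rule, and the bullet says only that the drug may be reintroduced. Its two options are outcomes that Table 3 assigns across grades: the same dose for a fully resolved Grade 2 event, and one lower for an incompletely resolved Grade 2 or a recovered Grade 3 event. On that reading the table selects within the bullet's permission. This is probably what the authors meant, but two things stand against it as a complete answer. Nothing in Section 6.6 says that the bullet is subject to the table. And the bullet's last sentence links a second reduction to a second occurrence, while Table 3 can require two levels after one event, so the bullet is not a faithful summary.

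The later bullet on re-escalation does not resolve the conflict. It governs a return to a higher dose after a reduction has been made, not the restart itself.

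A further objection is that under Appendix 13 adults enter the long-term extension once Amendment 6 is approved, with dosing by reference to Sections 6.1 and 6.7. That limits future adult cases. It leaves pediatric subjects still in the Treatment Phase, and it does not make the text consistent.

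Three stronger readings are tempting, and the documents do not support them:

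- A reader might add Grade 3 dry eye as an example, since Section 6.6.1.6 says "Withhold erdafitinib for Grade 3 toxicity" and gives no restart dose. But Section 6.6.1.5 sends many ocular symptoms to Table 15, which has a Grade 3 restart rule, so that example is contestable.
- A reader might fault the bullet for omitting medical-monitor input. Table 3's Grade 3 row requires none either, so this does not separate the two rules.
- A reader might argue from the bullet on holds over 28 days ("Erdafitinib may be re-started at the same or a lower dose") that bullets override Table 3. That bullet marks its departure as an exception and attaches conditions of benefit and medical-monitor concurrence. It is weak support for reading an unmarked bullet as an override.

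**Conclusion.** The point holds within its scope: Grade 3 erdafitinib-related toxicity with no Section 6.6.1 guideline, held 1 week or longer and recovered within 28 days. As written, Section 6.6 permits a restart dose that Table 3 does not allow. At one level the forgone reduction is 11.1% to 25.0%, or 3 mg in place of stopping for a child aged 6 to under 12. Where Table 3 requires two levels, even the bullet's lower option is one level too high.

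This rests on two assumptions: that drug-related toxicity in the bullet means the same as erdafitinib-related toxicity in Table 3, and that no precedence rule exists outside Section 6.6. None was found in the protocol.

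The documents give neither Grade 3 rates for these toxicities nor hold lengths, so the number of subjects affected is unknown. No efficacy analysis changes. The point should be corrected because it concerns dosing after severe toxicity and the correction is nearly free.

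**What to change.** Begin the 1-week bullet with the words *Subject to Table 3 and Section 6.6.1*. Limit its same-dose option to Grade 2 events, in line with the Table 3 Grade 2 row, and to events where Section 6.6.1 allows it, such as Grade 3 phosphate elevation in Table 8. Leave the exception for holds over 28 days unchanged.

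A minor edit can go with it. Footnote a to Table 3 reads "Please refer to Table 4", which covers only adults and adolescents aged 15 or over, while the bullets below cite Tables 4, 5 and 6. Extend the footnote to Tables 5 and 6.

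The cost is two wording changes in Section 6.6. They can go in an amendment, or in a clarification communication under Section 10.3.1 if current conduct does not change. Data collection, sample size and analyses are unaffected.

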6.6.1. Guidance for Specific Erdafitinib Toxicities

6.6.1.1. Guidelines for the Management of Elevated Phosphate Levels

Hyperphosphatemia will be graded as outlined in Table 7. Guidelines for the clinical management of elevated serum phosphate levels are presented in Table 8.

For guidance on Cycle 1 up-titration, see Section 6.1.

Adverse Event	Grade 1	Grade 2	Grade 3	Grade 4
Hyperphosphatemia	5.50-6.99 mg/dL 1.75-2.24 mmol/L	7.00-8.99 mg/dL 2.25-2.90 mmol/L	9.00-10.00 mg/dL (2.91-3.20 mmol/L), or asymptomatic soft tissue calcification with any phosphate level	>10.00 mg/dL (>3.20 mmol/L), or symptomatic soft tissue calcification with any phosphate level

 Table 7:
 Grading of Hyperphosphatemia Adverse Events

Serum Phosphate	Innes for Management of Serum Phosphate Ele	
Level	Study Drug Management	Symptom Management
<5.50 mg/dL	Continue erdafitinib treatment.	None.
(<1.75 mmol/L)		
(Grade 0)		
5.50-6.99 mg/dL	Continue erdafitinib treatment.	Restriction of phosphate intake to 600 –
(1.75-2.24		800 mg/day.
mmol/L)		
(Grade 1)	a	
7.00-8.99 mg/dL	Continue erdafitinib treatment.	Restriction of phosphate intake to 600 –
(2.25-2.90		800 mg/day.
mmol/L)	A dose reduction will be implemented for	
(Grade 2)	persistent ^a hyperphosphatemia (defined as serum phosphate ≥7.00 mg/dL for a period of 2 months) or if clinically necessary (eg, in the presence of additional adverse events linked	Adults: Start sevelamer 800 to 1,600 mg TID with food until phosphate level is <7.00 mg/dL.
	to hyperphosphatemia or electrolyte disturbances)	Children and adolescents: Start sevelamer 400 mg TID for BSA 0.75 m ² , 800 mg
		TID for BSA ≥ 0.75 to $<1.2 \text{ m}^2$, and 1,600 mg for BSA $\geq 1.2 \text{ m}^2$ with food. Titrate up/down by 200 mg for BSA 0.75 m ² , 400 mg TID for BSA ≥ 0.75 to $<1.2 \text{ m}^2$, and 800 mg for BSA $\geq 1.2 \text{ m}^2$ until phosphate level is $<7.00 \text{ mg/dL}$. ^b
9.00-10.00 mg/dL (2.91-	Withhold ^c erdafitinib treatment until serum phosphate level returns to 7.00 mg/dL (weekly	Restriction of phosphate intake to 600 – 800 mg/day.
3.20 mmol/L)	testing recommended).	
(Grade 3)	Re-start treatment at the same dose level.	Adults: Sevelamer up to 1,600 mg TID with food until serum phosphate level
	A deservation will be implemented for	returns to $<7.00 \text{ mg/dL}$.
	A dose reduction will be implemented for persistent ^a hyperphosphatemia (defined as serum phosphate ≥9.00 mg/dL for a period of 1 month) or if clinically necessary (eg, in the presence of additional adverse events linked to hyperphosphatemia or electrolyte disturbances)	Children and adolescents: Start sevelamer 400 mg TID for BSA 0.75 m ² , 800 mg TID for BSA \geq 0.75 to <1.2 m ² , and 1,600 mg for BSA \geq 1.2 m ² with food. Titrate up/down by 200 mg for BSA 0.75 m ² , 400 mg TID for BSA \geq 0.75 to <1.2 m ² , and 800 mg for BSA \geq 1.2 m ² until phosphate level is <7.00 mg/dL. ^b
>10.00 mg/dL (>3.20 mmol/L) (Grade 4)	Withhold ^c erdafitinib treatment until serum phosphate level returns to 7.00 mg/dL (weekly testing recommended).	Medical management as clinically appropriate.
	Re-start treatment at the first reduced dose level.	
	If persistent ^a hyperphosphatemia $(\geq 10.00 \text{ mg/dL})$ for >2 weeks, erdafitinib should be discontinued permanently.	
Significant	Erdafitinib should be discontinued	Medical management as clinically
alteration in baseline renal	permanently. (In situations where the subject is having clinical benefit and the investigator and the sponsor's medical monitor agree that	appropriate.

 Table 8:
 Guidelines for Management of Serum Phosphate Elevation

Serum Phosphate		
Level	Study Drug Management	Symptom Management
function or Grade 3	continuation of treatment is in the best interest	
hypocalcemia	of the subject, the drug may be re-started at	
	2 dose levels lower if appropriate. Follow	
	other recommendations described above,	
	Section 6.6.)	

 Table 8:
 Guidelines for Management of Serum Phosphate Elevation

Note: These are general guidelines that are based on emerging data and consensus experience of participating investigators or the experts in the field. The treating physicians must use clinical judgment and local standard of care to decide the best way to manage phosphate elevation. If sevelamer hydrochloride (Renagel[®]) is not available, use of other phosphate binders (non-calcium containing) based on the local standard is recommended, including sevelamer carbonate (Renvela) or lanthanum carbonate (Fosrenol[®]). These guidelines will be updated based on emerging data. Additional information on phosphorous in foods by class of food can also be found at www.permanente.net/homepage/kaiser/pdf/42025.pdf. Additional information for phosphate management and diet can be found at the National Kidney Foundation website (http://www.kidney.org/atoz/content/phosphorus.cfm).

a. Persistent hyperphosphatemia is considered to be more than 1 sequential phosphate value above the cut-off.

b. Pediatric dosing for sevelamer based on Fathallah-Shaykh 2018.

c. Study drug interruptions for hyperphosphatemia suggested to be 7 days in duration.

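### Protocol Tables 7, 8 and 3 give incompatible drug instructions for soft tissue calcification when serum phosphate is below 9.00 mg/dL

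*Protocol*

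**What the plan says.** Protocol Section 6.6.1.1 divides the work between two tables: "Hyperphosphatemia will be graded as outlined in Table 7. Guidelines for the clinical management of elevated serum phosphate levels are presented in Table 8".

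Table 7 gives Grades 3 and 4 two routes each. One is a phosphate range (9.00 to 10.00 mg/dL for Grade 3, above 10.00 for Grade 4). The other is calcification: "asymptomatic soft tissue calcification with any phosphate level" for Grade 3, "or symptomatic soft tissue calcification with any phosphate level" for Grade 4.

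Table 8 lists its hyperphosphatemia rows by serum phosphate and attaches a grade to each: below 5.50 mg/dL is Grade 0, 5.50 to 6.99 Grade 1, 7.00 to 8.99 Grade 2, 9.00 to 10.00 Grade 3, above 10.00 Grade 4. The first three rows say "Continue erdafitinib treatment". The last two say to withhold "erdafitinib treatment until serum phosphate level returns to 7.00 mg/dL". After that the Grade 3 row resumes at the same dose, and the Grade 4 row says "Re-start treatment at the first reduced dose level". Footnote c suggests 7 days for such interruptions. One further row is not tied to phosphate; it covers renal function and hypocalcemia. Calcification appears nowhere in Table 8.

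Section 6.6 makes Table 3 the general rule for erdafitinib-related toxicity by grade, then adds: "For eye, skin/nail, dry mouth/mucositis, and phosphate toxicity, specific recommendations in the management guidelines are provided in Section 6.6.1".

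**The concern.** Table 8 works as long as phosphate range and grade label coincide. Calcification separates them, because Table 7 assigns Grade 3 or 4 at any phosphate value. The site then has a subject whose phosphate points to one row of Table 8 and whose grade points to another, with Table 3 as a third candidate.

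What is at stake is first the handling of a severe event: the same subject could be kept on drug, held, or taken off permanently, each with support in the text. There is a smaller effect on the safety tables. The SAP lists hyperphosphataemia among adverse events of clinical importance (Section 6.1.3), summarises dose adjustments with reasons (Section 4.4), and tabulates events leading to modification, interruption or discontinuation (Section 6.1.1). If sites read the tables differently, those counts would partly reflect the reading chosen.

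**Working it through.** No arithmetic applies. The check follows one subject through each table.

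**Inputs.** Grade from Table 7; action from Table 8, read once by phosphate row and once by grade label; action from Table 3 by grade. All are in Protocol Sections 6.6 and 6.6.1.1.

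**Example: phosphate 6.0 mg/dL.**

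| Reading | Asymptomatic calcification (Grade 3 by Table 7) | Symptomatic calcification (Grade 4 by Table 7) |
|---|---|---|
| Table 8, row 5.50 to 6.99 mg/dL | Continue | Continue |
| Table 8, row bearing the grade | Hold until phosphate is 7.00 (already below it; 7 days suggested), then same dose | Hold until phosphate is 7.00 (already below it; 7 days suggested), then first reduced dose |
| Table 3, by grade | Interrupt; restart one or two doses lower on recovery within 28 days; discontinue if unresolved for more than 28 days | Discontinue |

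**Range affected.**
- Below 7.00 mg/dL: as in the table. The row below 5.50 mg/dL also says continue.
- 7.00 to 8.99 mg/dL: the row still says continue, with a dose reduction if phosphate stays at or above 7.00 for 2 months or if clinically necessary. The grade label says hold. Above 7.00 exactly, the release value has not yet been reached. Table 3 is unchanged.
- From 9.00 mg/dL upward every Table 8 row withholds, so the continue reading drops out. The conflict described here therefore applies below 9.00 mg/dL.

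**Text that might settle it.**
- Permanent discontinuation in the Grade 4 row of Table 8 requires phosphate of at least 10.00 mg/dL for more than 2 weeks. It cannot be met below 9.00, so the instruction to discontinue comes from Table 3 alone.
- The allowance for additional adverse events linked to hyperphosphatemia is only in the Grade 2 and Grade 3 rows and leads only to a dose reduction. Under Table 7 calcification itself sets the grade, so it is not clearly an additional event.
- Section 6.6 names Table 3 and then points to Section 6.6.1, without saying which prevails for an event that Table 8 does not list.

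**The case against.** The best counter-argument is that this is a gap with a default. Table 8 is about raised serum phosphate and its first column is phosphate level. It is silent on calcification, so the general rule in Table 3 applies. On that view, using the row above 10.00 mg/dL for a subject at 6.0 mg/dL because of a bracketed grade label is strained. This is a sensible way to resolve the matter, but the protocol does not state it. Section 6.6.1.1 treats calcification as a grade of hyperphosphatemia and sends hyperphosphatemia to Table 8. Setting the label reading aside still leaves continue (Table 8 row) against interrupt or discontinue (Table 3).

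The protocol also leaves room for judgment. The note to Table 8 calls its contents general guidelines and defers to the treating physician, and Section 7.1 requires stopping when the investigator believes safety calls for it. No site is bound to keep treating a subject with symptomatic calcification. That stands and lowers the risk, but it does not make the tables agree.

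A reader might infer three stronger things that the documents do not support:
- That under Table 8 the hold lasts zero days and the drug restarts immediately. The phosphate condition is indeed already met below 7.00 mg/dL, but footnote c suggests 7-day interruptions.
- That the calcification grades were written to catch harm in subjects whose phosphate a binder has lowered. No section states that purpose.
- That the main results are threatened. The study is single-arm, its primary endpoint is response rate by independent review, and no calcification events are documented.

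**Conclusion.** The inconsistency is real and in the current text. For calcification with phosphate below 9.00 mg/dL the protocol supports incompatible actions: continue, hold and resume (same dose for Grade 3, first reduced dose for Grade 4), or the Table 3 action (interrupt and restart lower, or discontinue if unresolved, for Grade 3; discontinue for Grade 4). This goes beyond missing detail, because stated rules disagree in the two most severe grades of Table 7.

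Few subjects are likely to be affected. Section 4.3 reports no soft tissue calcification at 9 mg daily in the completed Phase 1 study and no such abnormalities in the ongoing Phase 2 study. The documents give no expected frequency for this trial, so none is assumed. The conclusion rests only on reading the three tables as printed and on Section 6.6 giving no order of precedence. It is a safety-instruction point that should be corrected. It does not bear on the efficacy analysis, and it implies no view on which action is clinically right.

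**What to change.** Reconcile Tables 3, 7 and 8 for soft tissue calcification and state which table governs, so that each combination of grade and phosphate value leads to one instruction. This could be an entry for calcification in Table 8, which already has one row not tied to phosphate, or a sentence in Section 6.6 or 6.6.1.1 naming the governing table. The action and any restart rule are for the sponsor's clinical team.

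The cost is one row or one sentence, with no added assessments. Under Section 10.3.1 a protocol clarification communication is enough if study conduct does not change; otherwise an amendment is needed.

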Instructions for up-titration of erdafitinib, in the absence of erdafitinib related toxicity, based on the serum phosphate level at Cycle 1 Day 14 are provided below and in Figure 5. For children aged ≥ 6 to <12 years and adolescents aged ≥ 12 to <15 years, an additional blood sample will be drawn at Cycle 2 Day 7 for determination of the serum phosphate level and the need for dose modification.

Subjects with a serum phosphate level higher than 9.00 mg/dL (>2.91 mmol/L) will withhold erdafitinib treatment, with at least weekly assessment of serum phosphate until it returns to less than 7.00 mg/dL (<2.25 mmol/L) while initiating treatment with a phosphate binder such as sevelamer (see Table 8 for detailed guidelines regarding further treatment).

[figure not shown]

Figure 5: Instructions for up-titration of erdafitinib based on serum phosphate levels

Note: in presence of erdafitinib-related toxicities, the investigator may choose to maintain the same dose of erdafitinib without up-titration.

Adult subjects and adolescent subjects aged ≥ 15 to <18 years

- Adult subjects and adolescent subjects aged ≥15 to <18 years with a serum phosphate level between 7.00 to 8.99 mg/dL (2.25 mmol/L to 2.90 mmol/L) on Cycle 1 Day 14 will increase the erdafitinib dose from 8 mg once daily to 9 mg once daily, while concurrently initiating treatment with a phosphate binder such as sevelamer (see Table 8 for details).
- Adult subjects and adolescent subjects aged ≥15 to <18 years with a serum phosphate level less than 7.00 mg/dL (<2.25 mmol/L) will increase the erdafitinib dose to 9 mg once daily. No concomitant treatment is required for these subjects.

Adolescent subjects aged ≥ 12 to <15 years

- Adolescent subjects aged ≥12 to <15 years with a serum phosphate level between 7.00 to 8.99 mg/dL (2.25 mmol/L to 2.90 mmol/L) will increase the erdafitinib dose from 5 mg once daily to 6 mg once daily on Cycle 1 Day 14 or Cycle 2 Day 7, and further from 6 mg once daily to 8 mg once daily on Cycle 2 Day 7 (for those already up-titrated to 6 mg on Cycle 1 Day 14), while concurrently initiating treatment with a phosphate binder such as sevelamer (see Table 8 for details). This 2-step up-titration is step-wise, ie, no subjects will be allowed to directly up-titrate from 5 mg to 8 mg.

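### The paired mg/dL and mmol/L phosphate cut-offs are not equivalent, so samples in three narrow bands get a different grade, and sometimes a different action, depending on the reporting unit

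*Protocol*

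**What the plan says.** Protocol Table 7 defines the hyperphosphatemia grades in both units:

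- Grade 1: "5.50-6.99 mg/dL 1.75-2.24 mmol/L"
- Grade 2: "7.00-8.99 mg/dL 2.25-2.90 mmol/L"
- Grade 3: "9.00-10.00 mg/dL (2.91-3.20 mmol/L), or asymptomatic soft tissue calcification with any phosphate level"
- Grade 4: ">10.00 mg/dL (>3.20 mmol/L), or symptomatic soft tissue calcification with any phosphate level"

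Table 8 attaches actions to the same bands. Dietary phosphate restriction begins at Grade 1 and the binder at Grade 2. Erdafitinib is withheld at Grades 3 and 4. After withholding, the Grade 3 row says "Re-start treatment at the same dose level" and the Grade 4 row says "Re-start treatment at the first reduced dose level".

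Section 6.1 reuses two of the pairs. "Subjects with a serum phosphate level higher than 9.00 mg/dL (>2.91 mmol/L) will withhold erdafitinib treatment", and withholding ends once phosphate is "less than 7.00 mg/dL (<2.25 mmol/L".

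Protocol Appendix 2 assigns serum chemistry, including phosphate, to the local laboratory. Neither document fixes the reporting unit, gives a conversion factor, or says which unit prevails when the two disagree.

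**The concern.** One analyte has one conversion factor. If the two halves of a pair are not the same concentration, a sample lying between them meets the criterion in one unit and misses it in the other. Sites read whichever unit their laboratory reports, so two such samples with the same true phosphate could be graded and managed differently.

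The most consequential case is the Grade 3/4 boundary, where the restart dose changes by one level. For a child aged 6 to under 12 who stayed at 3 mg, Table 6 lists stopping as the first reduction, so there the unit would separate restarting from stopping. At the Grade 1/2 boundary the difference is binder start and the Section 6.1 test for ending withholding. At the Grade 0/1 boundary it is dietary restriction.

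In the analysis, the discrepancy can enter through investigator-assigned grades that follow Table 7 and through the dose-adjustment summaries in SAP Section 4.4.

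**Working it through.** **Step 1: the documents' own figures, no outside constant.** The inputs are the four pairs in Table 7. For a mg/dL cut-off a and a mmol/L value b printed to two decimals, the factor (mmol/L per mg/dL) that would produce b lies between (b − 0.005)/a and (b + 0.005)/a.

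| Pair (mg/dL / mmol/L) | Lower limit | Upper limit |
|---|---|---|
| 5.50 / 1.75 | 1.745/5.50 = 0.3173 | 1.755/5.50 = 0.3191 |
| 10.00 / 3.20 | 3.195/10.00 = 0.3195 | 3.205/10.00 = 0.3205 |
| 7.00 / 2.25 | 2.245/7.00 = 0.3207 | 2.255/7.00 = 0.3221 |
| 9.00 / 2.91 | 2.905/9.00 = 0.3228 | 2.915/9.00 = 0.3239 |

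No two ranges overlap. If the mg/dL figures are also allowed ±0.005, the 5.50/1.75 range ends at 1.755/5.495 = 0.3194 and the 9.00/2.91 range starts at 2.905/9.005 = 0.3226. There is still no factor common to all four pairs.

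**Step 2: which pairs agree.** The documents give no factor, so one is assumed: 10/M with M = 30.974 g/mol for phosphorus, that is 3.0974 mg/dL per mmol/L.

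- From mg/dL: 5.50/3.0974 = 1.776; 7.00/3.0974 = 2.260; 9.00/3.0974 = 2.906; 10.00/3.0974 = 3.229 mmol/L.
- From mmol/L: 1.75 × 3.0974 = 5.42; 2.25 × 3.0974 = 6.97; 2.91 × 3.0974 = 9.01; 3.20 × 3.0974 = 9.91 mg/dL.

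Only 9.00/2.91 is reproduced at two decimals. With M rounded to 31.0 the four mmol/L values are 1.774, 2.258, 2.903 and 3.226. The other three pairs still fail, and 9.00 then rounds to 2.90. These figures show the mismatch only; they are not suggested thresholds.

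**Step 3: samples graded differently**, with M = 30.974 and both units at the two decimals printed in Table 7:

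| Result in mmol/L | Same sample in mg/dL | Grade by mmol/L | Grade by mg/dL | What differs |
|---|---|---|---|---|
| 1.75–1.77 | 5.42–5.48 | 1 | 0 | Dietary restriction |
| 2.25 | 6.97 | 2 | 1 | Binder start; end of withholding (Section 6.1) |
| 3.21–3.22 | 9.94–9.97 | 4 | 3 | Restart at the first reduced level or at the same level |

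A result of 3.23 mmol/L is 10.005 mg/dL, a rounding tie. In each row the mmol/L scale gives the higher grade. In true concentration the bands are 5.405–5.495, 6.954–6.995 and 9.927–10.005 mg/dL, so about 0.09, 0.04 and 0.08 mg/dL wide. At 9.00/2.91 only a rounding sliver of about 0.003 mg/dL is discordant.

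**Step 4: share of readings.** The documents give no on-treatment phosphate distribution. Assuming a normal distribution with SD 1.2 mg/dL and mean 5.5 to 6.5 mg/dL, the bands contain 2.0% to 3.0%, 0.6% to 1.3%, and 0.003% to 0.04% of readings.

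**The case against.** The strongest reply is that little turns on this. The bands are narrow and the restart-dose band is very rarely hit. The notes to Table 8 call it general guidance and leave management to clinical judgment. The CRF and its guidelines are not available here and may already fix a unit or a conversion. All of this limits the practical effect, and the CRF point cannot be excluded. None of it reconciles the printed scales, and grading by Table 7 is not left to discretion.

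A reader might also infer more than the documents support:

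- **Up-titration depends on the unit.** It does not at 7.00/2.25: in Section 6.1, subjects below 7.00 and those at 7.00–8.99 mg/dL take the same dose step, and only the binder differs.
- **The decision to withhold depends on the unit.** The 9.00/2.91 pair agrees to rounding under the 30.974 factor.
- **A result of 2.25 mmol/L counts toward the two-month dose-reduction rule.** Table 8 states its persistence rules in mg/dL only, and 6.97 mg/dL does not meet that one. Its binder target is also in mg/dL only.
- **Section 6.1 has a unit error at exactly 2.91 mmol/L.** That is a boundary gap, not a conversion error. It also occurs at exactly 9.00 mg/dL, and Table 8 covers it as Grade 3.
- **The SAP carries the mmol/L cut-offs into its tables because it reports in SI units.** SAP Section 6.2 grades laboratory results by NCI-CTCAE version 5.0, not Table 7, and the phosphate subgroup in SAP Table 2 is in mg/dL.
- **Dose would differ systematically by country, or hyperphosphatemia being common (77% in the Phase 2 urothelial study) makes the problem common.** That figure is any hyperphosphatemia and says nothing about readings inside the bands.

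**Conclusion.** The point holds in a limited form. The four printed pairs cannot all be equivalent, and this follows from the protocol's own numbers. Samples just below 5.50, 7.00 and 10.00 mg/dL can receive a different investigator-assigned grade according to the unit reported. The consequences are, in turn, dietary restriction, binder start or the end of withholding, and restart dose.

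The effect is small: about 2–3%, about 1% and under 0.1% of readings at the three boundaries. Those shares rest entirely on the assumed distribution. The exact discordant values rest on the assumed molar mass and on two-decimal reporting. A laboratory giving mg/dL to one decimal would shift which values disagree; 2.25 mmol/L, for example, would become 7.0 mg/dL and Grade 2 on both scales.

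The primary response-rate analysis is not directly affected. What can be affected is hyperphosphatemia grade and individual dose modification. The correction is worth making because the inconsistency is certain, a dose rule is involved, and the change is cheap.

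**What to change.** Reconcile the paired values across Section 6.1, Table 7 and Table 8, and state which unit governs. Convert every phosphate result to that unit in the eCRF, with one stated factor and rounding rule, before Table 7 grades and Table 8 actions are applied. If the CRF guidelines already do this, cite the rule in the protocol. Which thresholds are clinically intended is for the sponsor, and none is proposed here.

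The cost is a few table entries, one sentence on the governing unit and one eCRF derivation. No new assessment or sample is needed.
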